7.13.5 Pregnancy

Pregnancy itself is not regarded as an AE.

If there is a pregnancy during the study period, the subject must be withdrawn from any following study treatment but should continue to be followed within the study and the outcome of pregnancy must be reported even if the delivery occurs after study completion.

A pregnancy confirmed during the study period must be reported by the Investigator on a Pregnancy Report Form immediately upon acknowledge and be submitted to the Sponsor according to contact details specified in Section 7.13.2. The report can be prospective or retrospective. Follow-up shall be conducted to obtain outcome information on all prospective reports.

Cases that led to fetal distress, fetal death or a congenital abnormality or birth defect are to be regarded as SAEs and shall be reported on the Exposure *in utero* Report Form to the Sponsor immediately but no later than 24 hours after the Investigator's awareness. These events shall be handled as SAEs during data processing. Other complications during the pregnancy that are related to the pregnant woman and fulfils any serious criteria, such as pre-eclampsia requiring hospitalization, shall be reported, and handled as SAEs. Elective abortions without complications shall not be reported as AEs.

7.14 Stopping rules

Enrollment and treatment in the study will be temporarily halted if a SAE occurs for the following:

- any unanticipated SAE which is possibly related to the study device or procedure including but not limited to a vascular embolic event that leads to skin necrosis, vision loss or stroke, damage to facial nerves which may result in facial paralysis or injury to internal facial structures.

The SAE will be investigated by the Sponsor. If the Sponsor's investigation concludes the SAE:

CONFIDENTIAL

Effective date: 2023-05-24 22:48

- was unanticipated,
- directly related to the investigational device or device injection procedure, and
- presents an unreasonable risk to study subjects,

the study will be terminated, and the Investigators notified. The IRB and RA will also be notified if the study is prematurely terminated due to safety concerns.

If the SAE does not meet the above criteria, then enrollment in the study will continue provided all other safety criteria have been met.

8. DESCRIPTION OF STUDY VISITS

All study visits and assessments are described in the sections below and outlined in the schedule of events in Table 1.

A written signed informed consent (incl. Health Insurance Portability and Accountability Act of 1996 [HIPAA] and photo consent) must be obtained prior to performing any study related evaluations and/or procedures. The subject must be provided with a fully completed dated and signed copy.

8.1 Screening/Visit 1a

The following activities and screening assessments will be performed within 21 days prior to the baseline⁶ (Day 1) visit (Table 1):

- Obtain informed consent.
- Record the subject's medical history (including any prior dermatological procedures or implants, see Section 4.2) and previous or concomitant therapies (see Section 4.3).
- Obtain demographic data: Month and year of birth, sex at birth, gender identity, race, ethnicity, and FST. For determination of the FST, see Table 4.
- For all females of childbearing potential, obtain a UPT.
 - The test result must be negative for the subject to be eligible for study participation and prior to receiving any study treatment.
- Assessment of GCRS – Treating Investigator and Blinded Evaluator (see Section 6.3).
- Perform visual function assessments (see Section 7.6).
- Perform palpability assessments (see Section 7.4).
- Perform sensory tests (see Section 7.2).
- Perform functionality tests (see Section 7.3).
- Assess eligibility (inclusion and exclusion criteria).
- Schedule the baseline/Day 1 visit or proceed to Day 1 activities if the subject meets all eligibility criteria.

⁶ The screening and baseline visits can be combined.

Table 4 Fitzpatrick Skin Type (FST)

Skin type	Skin color	Skin characteristics
I	White; very fair; red or blond hair; blue eyes; freckles	Always burns, never tans
II	White; fair; red or blond hair; blue, hazel or green eyes	Usually burns, tans with difficulty
III	Cream white; fair with any eye or hair color; very common	Sometimes mild burn, gradually tans
IV	Brown; typical Mediterranean Caucasian skin	Rarely burns, tans with ease
V	Dark brown; Middle Eastern skin types	Very rarely burns, tans very easily
VI	Black	Never burns, tans very easily

Fitzpatrick Skin Type (FST) is a skin classification system that categorizes different skin colors, and their reactions to ultraviolet light.⁹

8.2 Baseline/Initial treatment/Visit 1b

The screening visit and the baseline visit may be performed on the same day if the subject is deemed eligible by the Treating Investigator.

If the screening and baseline visits are not performed on the same day, the following procedures should be repeated at the baseline visit (Table 1) **prior to treatment**:

- Review for changes in medical history and concomitant therapies.
- Re-confirm eligibility (inclusion and exclusion criteria).
- Perform UPT for all females of childbearing potential
 - The test result must be negative for the subject to be eligible for treatment.
- Assessment of GCRS – Treating Investigator and Blinded Evaluator (see Section 6.3).
- Perform sensory tests (see Section 7.2).
- Perform functionality tests (see Section 7.3).
- Perform palpability assessments (see Section 7.4).
- Perform visual function assessments (see Section 7.6).
 - If a subject is considered to have abnormal vision per the exclusion criteria, the subject is not eligible for the study.

Once the subject is deemed eligible for study treatment by the Treating Investigator, the following procedures should be completed:

- Record subject's height and weight.
- Randomization to treatment with *Restylane Lyft with Lidocaine* (Investigational Group) or *Juvéderm Voluma XC* (Comparator Group).
- Obtain pre-treatment/baseline photographs of the chin area.

Effective date: 2023-05-24 22:48

Effective

- Obtain pre-treatment/baseline responses to the FACE-Q™ Satisfaction with chin questionnaire (see Section 6.9).
- Obtain pre-treatment/baseline responses to the FACE-Q™ Satisfaction with lower face and jawline questionnaire (see Section 6.10).
- Pre-treatment pain assessment using the NPS (prior to application of any anesthetic) (see Section 7.1).
- Subjects will be injected with either *Restylane Lyft with Lidocaine* (Investigational Group) or *Juvéderm Voluma XC* (Comparator Group) in the chin area. After injection, the following should be performed:
 - Immediately following injection, subject should complete the post-treatment pain assessment using the NPS (see Section 7.1). This should be completed before any post-injection therapies are provided.
 - Approximately 30 minutes after injection, perform visual function assessments - post-treatment (see Section 7.6).
 - Record all concomitant medications/procedures used prior, during or after the injection session.
 - Record the following injection details:
 - Date and time of completed injection
 - Lot number
 - Number of syringes used
 - Volume of study product used
 - Needle or cannula used for supraperiosteal or subcutaneous injections
 - Injection method and depth of injection
 - Additional local or topical anesthesia used
 - Evaluate for device deficiencies. If any device deficiency is noted, complete the procedures as specified in Section 7.13.4.

CCI

- Evaluation of post-injection AEs by Treating Investigator.
- Schedule the follow-up telephone call (Visit 2) 72 hours (± 24 hours) and the follow-up visits (Visit 2a) at 14 days (2 weeks; +7 days) and (Visit 3) 1 month (4 weeks; +7 days) after the baseline visit (Visit 1b).

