5.3.3 Post-treatment care

When the injection is completed, the treated area may be gently molded or massaged to avoid any irregularities.

Brisk molding or massaging should be avoided in order to prevent undue swelling of the region.

Post treatment procedures with ice pack is allowed as per investigator normal procedure. Ice pack can be applied for a short period if the treated area is swollen.

After the injection, some common injection-related reactions might occur. These reactions include redness, swelling, pain, itching, bruising or tenderness at the implant site. Typically, resolution is spontaneous within two to four weeks after injection into the skin.

Any medication or therapy used by the subject must be recorded in the eCRF.

Subjects will be asked to:

- Avoid heat (sunbathing, sauna, steam baths, etc.) or extreme temperatures until any signs of local inflammation have disappeared.

GALDERMA

Title
43USCH2208, Clinical Investigation Plan R Lyft Chin US

Doc id

MA-52558

Effective date: 2023-05-24 22:48

- Avoid touching or shaving the treated area and not to apply any creams or cosmetics in the treated area before the skin has healed completely in order to prevent infections or elicit an inflammatory reaction.
- Abstain from prohibited medications, treatments and procedures (see Section 4.3.4).
- Contact the study center if common injection-related reactions such as bruising, redness, pain, tenderness, lumps/bumps, itching, swelling at the injection site, have not diminished within two weeks or if they get worse.
- Contact the study center if they have signs of infection and/or inflammation such as pain, tenderness, heat, redness, swelling, small lumps that contain pus or yellowish fluid, and fever. These symptoms can occur within days or several weeks after treatment.

Subjects treated with the comparator *Juvéderm Voluma XC*, should also avoid strenuous exercise within the first 24 hours of treatment. Please refer to post-treatment recommendation in the IFU provided with the product.

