5.6 Blinding

The Treating Investigator will not be blinded to study treatments.

A Blinded Evaluator, to whom randomization and treatment are concealed, will conduct the blinded assessments. As much as possible, the same Blinding Evaluator should assess a particular subject throughout the study.

The Blinded Evaluator is not allowed to be present during the injections or to discuss treatments with the Treating Investigator or subjects. All documents with information regarding study products

Effective date: 2023-05-24 22:48

Effective date:

Effective

Version: 4.0

and randomization assignment should be kept in a separate binder not available to the Blinded Evaluator.

Safety assessments will be performed by non-blinded personnel.

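### Protocol 8.2 lists the baseline FACE-Q questionnaires after randomization, and no readable passage masks the subject or delays disclosure of the product

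*Protocol*

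**What the plan says.** Protocol 8.2 opens the relevant list with "Once the subject is deemed eligible for study treatment by the Treating Investigator, the following procedures should be completed". The items then run:

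1. height and weight;
2. "Randomization to treatment with" one of the two products;
3. baseline photographs;
4. "Obtain pre-treatment/baseline responses to the FACE-Q™ Satisfaction with chin questionnaire";
5. "Obtain pre-treatment/baseline responses to the FACE-Q™ Satisfaction with lower face and jawline questionnaire";
6. the pre-treatment NPS, taken before any anesthetic;
7. the injection, followed by the post-injection steps.

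The numbers are mine; the protocol uses bullets.

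On masking, Protocol 5.6 says "The Treating Investigator will not be blinded to study treatments" and "A Blinded Evaluator, to whom randomization and treatment are concealed, will conduct the blinded assessments". It does not state the subject's own status. Protocol 5.3.3 adds that subjects given the comparator "should also avoid strenuous exercise within the first 24 hours of treatment".

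SAP 4.4 defines baseline, for all analyses, as the last value recorded before product is first given. SAP 10.3 plans a descriptive summary of the change in pain from before to after injection.

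**The concern.** A baseline is safe from the allocation only if it is recorded before the allocation can be known to the person giving the answer. As listed, a site that works down Protocol 8.2 draws the allocation first and then hands the subject two satisfaction questionnaires. The injector, who is in contact with the subject, knows the product by then, and no rule governs disclosure. A subject who is pleased or disappointed with the assigned product could answer differently, and SAP 4.4 would accept that answer as baseline.

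At stake are any subject-reported changes from baseline. Protocol 2.2 describes the subject's perspective as critical in studies of this kind, so the subject-reported baselines deserve the same protection by order that the plan gives to the GCRS.

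**Working it through.** The plan gives no figure on this point, so there is none to reproduce. The check compares passages and then does one piece of algebra.

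**1. Order of the baselines.**

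| Baseline | Where listed | Relative to randomization |
|---|---|---|
| GCRS, both assessors | Protocol 8.1, and the repeat list in 8.2 that comes before eligibility is settled | Before |
| FACE-Q chin | Protocol 8.2, second list | After |
| FACE-Q lower face and jawline | Protocol 8.2, second list | After |
| Pre-treatment NPS | Protocol 8.2, second list | After |
| Photographs | Protocol 8.2, second list | After |

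The second list broadly follows the course of the visit, through injection to a vision check about 30 minutes later. A site would naturally follow it as written.

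**2. Who can know the product.** The allocation is concealed from the Blinded Evaluator and known to the Treating Investigator. No readable passage masks the subject or sets a time for disclosure. Protocol 5.6 also bars the evaluator from discussing treatment with subjects. That precaution would be largely unnecessary if subjects could never know.

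**3. What the analysis accepts as baseline.** SAP 4.4 refers to first administration, not to randomization. A FACE-Q answer given between the two events qualifies.

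**4. Size of the effect.** Let knowledge of the product move mean baseline in one arm by s points more than in the other, and leave follow-up scores unchanged.

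- Unadjusted change: the between-arm difference in (follow-up minus baseline) moves by −s.
- Baseline-adjusted: it moves by about −b × s, where b is the slope of follow-up on baseline.

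The documents give neither s nor b. With assumed values of b from 0.3 to 0.7:

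| Assumed s | Unadjusted | Adjusted, b = 0.3 | Adjusted, b = 0.7 |
|---|---|---|---|
| 1 | −1 | −0.3 | −0.7 |
| 2 | −2 | −0.6 | −1.4 |
| 5 | −5 | −1.5 | −3.5 |

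These rows show how the effect scales. They do not predict its size.

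**5. Which endpoints it reaches.**

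- The primary endpoint uses the Blinded Evaluator's GCRS, recorded before randomization. It is not affected.
- The FACE-Q baselines are exposed. Whether a FACE-Q change score is analyzed can only be inferred from the baseline label and the general rule in SAP 4.4, because Protocol 6.9 and 6.10 and any matching SAP text are not readable.
- The NPS change is planned, but the first score precedes any anesthetic or injection, and it is hard to see how a product name would alter it.
- Photographs are standardized (Protocol 6.1), and there is little reason for the allocation to change them.

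**The case against.** The strongest reply is that the problem is inferred at several steps. Most of that reply stands as a limit on the claim.

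- **Fixed sequence.** A reader might infer that Protocol 8.2 mandates this order. It does not: the list is unnumbered, and timing is stated on individual items where it matters. The item on medications used before, during or after the injection session sits below the 30-minute vision check. A site may complete the FACE-Q before drawing the allocation and still comply.
- **Unmasked subjects.** A reader might take the comparator-only exercise advice as proof that subjects know their product at baseline. That advice is post-treatment care, so it shows only that the product could be inferred after injection. The counseling before treatment in Protocol 5.3.1 names both products and does not point to arm-specific disclosure.
- **Damage to a covariate, or a spurious difference at every follow-up visit.** The readable text supports neither. The only baseline covariate in the primary model (SAP 9.1.2) is GCRS, and no FACE-Q model or visit schedule can be read.
- **Little weight in the conclusions.** SAP 9.2 offers p-values beyond the primary endpoint only as an aid to interpretation and treats the other secondary analyses as descriptive. Both products are 20 mg/mL hyaluronic acid gels with 0.3% lidocaine, so a strong reaction to the assignment is not evident.
- **Incomplete cure.** If subjects do know the product, their follow-up answers are exposed as well, and re-ordering the baseline does not change that.

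What the reply does not remove is the gap itself. The listed order permits a FACE-Q baseline given with knowledge of the allocation, no readable passage prevents it, and the SAP would accept it. Descriptive status does not take bias out of a reported estimate.

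**Conclusion.** The point holds as a minor, free improvement. The plan as listed leaves open a route by which knowledge of the product could shift the FACE-Q baselines. The shift would pass in full into an unadjusted change and in part into an adjusted one. Its size and direction are unknown. It could be zero if sites complete the questionnaires first or do not disclose the product beforehand.

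The conclusion rests on three assumptions: that sites tend to follow the listed order, that some subjects learn the product before answering, and that FACE-Q is analyzed as a change from baseline. The documents make each plausible and confirm none. They do not support calling the subjects unmasked as a fact, or saying that bias has been shown. The primary GCRS comparison and the sample size are untouched, and any effect on the NPS or photographs is likely negligible.

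**What to change.** In the second list of Protocol 8.2, move the two baseline FACE-Q questionnaires above the randomization item, and move the pre-treatment NPS with them for convenience. Add one sentence stating that the allocation is obtained from the Interactive Response System only after these responses are recorded. Align the schedule of events and the site worksheet if they show the order.

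The cost is a re-ordering of bullets: same visit, same procedures, no added subjects or staff time.

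For subjects already randomized, SAP 6 lists the date and time of randomization. If questionnaire completion times were also captured, the sponsor can compare the two and report the actual order in the Clinical Study Report.

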8.3 Follow-up visits

8.3.1 Telephone call/Visit 2

The following should be completed at the telephone contact 72 hours (± 24 hours) after the Baseline/Initial treatment/Day 1 visit (Table 1):

Effective date: 2023-05-24 22:48

- Interview the subject regarding the Subject Diary completion and reported events since receiving treatment. Remind subject to complete the Subject Diary daily and bring it to the next on-site visit.
- Interview the subject regarding any concomitant therapies.
- Interview the subject regarding any AEs that have occurred since receiving treatment. If AEs are reported, notify the Investigator immediately and determine whether subject should return to the study center for an unscheduled visit. The Investigator should assess all reported AEs in a timely manner.
- Interview the subject regarding when (in hours after treatment) the subject felt comfortable returning to social engagements (public/social appearances) exemplified as returning to business office or other public workplace, having dinner in a public restaurant, attending a social event/gathering such as dinner party, etc.
- Remind the subject of the next scheduled on-site visit (Visit 2a), 14 days (2 weeks; +7 days) after the baseline visit (Visit 1b).

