8.3.2 Follow-up visit/Visit 2a

The following should be completed at the follow-up visit 14 days (+7 days) after the Baseline/Initial treatment/Day 1 visit (Table 1):

- Perform visual function assessments (see Section 7.6).
- Perform palpability assessments (see Section 7.4).
- Perform sensory tests (see Section 7.2).
- Perform functionality tests (see Section 7.3).
- Evaluate changes in facial hair growth in the treated area (see Section 7.5).
- Review of the Subject Diary. Remind subject to complete the Subject Diary daily and bring it to the next on-site visit.
- Obtain post-treatment photographs of the chin area.
- Interview the subject regarding any concomitant therapies.
- Interview the subject regarding any AEs that have occurred since last visit.
- Remind subject of the next scheduled on-site visit (Visit 3) 1 month (4 weeks; +7 days) after the baseline visit (Visit 1b).

8.3.3 Follow-up visit/Optional touch-up/Visit 3

The following should be completed at the follow-up visit 1 month (4 weeks; +7 days) after the Baseline/Initial treatment/Day 1 visit (Table 1):

- Assessments to be performed prior to optional touch-up if treatment will be given:
 - Assessment of GCRS – Treating Investigator (see Section 6.3).
 - Pre-treatment pain assessment using the NPS (prior to application of any anesthetic) (see Section 7.1).

Effective date: 2023-05-24 22:48

- Perform visual function assessments (see Section 7.6).
- Perform palpability assessments (see Section 7.4).
- Perform sensory tests (see Section 7.2).
- Perform functionality tests (see Section 7.3).
- Evaluate changes in facial hair growth in the treated area (see Section 7.5).

CCI

- Obtain pre-treatment photographs of the chin area.
- Interview the subject regarding any concomitant therapies.
- Interview the subject regarding any AEs that have occurred since last visit.

If touch-up is to be performed, the following should be confirmed/performed:

- Assess whether optimal aesthetic result has been achieved (as agreed by the Treating Investigator and subject) and determine whether optional touch-up is appropriate.
- Re-confirm eligibility (inclusion and exclusion criteria) – prior to treatment.
- Perform UPT for all females of childbearing potential (prior to treatment). Test result must be negative for the subject to be eligible for treatment.
- Optional touch-up treatment – subjects will be injected with the assigned study product. After injection, the following should be performed:

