8.3.4 Telephone call/Visit 3a (Subjects that received touch-up)

The following should be completed at the telephone contact 72 hours (± 24 hours) after touch-up (Table 1):

- Interview the subject regarding the Subject Diary completion and reported events since receiving treatment. Remind subject to complete the Subject Diary daily and bring it to the next on-site visit.
- Interview the subject regarding any concomitant therapies.
- Interview the subject regarding any AEs that have occurred since receiving treatment. If AEs are reported, notify the Investigator immediately and determine whether subject should return to the study center for an unscheduled visit. The Investigator should assess all reported AEs in a timely manner.
- Interview the subject regarding when (in hours after treatment) the subject felt comfortable returning to social engagements (public/social appearances) exemplified as returning to business office or other public workplace, having dinner in a public restaurant, attending a social event/gathering such as dinner party, etc.
- Remind the subject of the next scheduled on-site visit (Visit 3b), 14 days (2 weeks; +7 days) after the touch-up treatment (Visit 3).

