**3.2.4.9 Returning to Social Engagement**

A follow-up telephone call should be made 72 hours after each treatment, where the treated subject will be asked when (in hours after treatment) s/he felt comfortable returning to social engagement, such as returning to the office or other public workplace, having dinner in a public restaurant, attending a social event/gathering such as a dinner party, etc. cc

[figure not shown]
For each subject, time, in hours, until the subject feels comfortable returning to social engagement will be computed. A separate flag for each treatment will be created to determine the time in hours at which the subject responded they felt comfortable returning to social engagement. Time, in hours, until the subject feels comfortable returning to social engagement will be calculated as follows:

$$\text{Number of hours until subject feels comfortable returning to social engagement} = \text{Date and Hour of Response Flag} - \text{Date and Hour of Treatment}$$

Subjects who never feel comfortable returning to social engagement will be censored at 23:59 on the date of their telephone call visit (Visit 2a for initial treatment, Visit 3a for optional touch-up treatment). Subjects who felt comfortable returning to social engagement, but who provided a date, and no time will be censored at 23:59 on the date provided. Subjects who felt comfortable returning to social engagement, but who provided a time, and no date will be censored at the provided time on the date of their telephone call visit. Subjects who felt comfortable returning to social engagement, but who did not provide a date and time will be censored at 23:59 on the date of their telephone call visit. Subjects who never respond to the 72-hour phone call will be censored at 23:59 on the target date of their telephone call visit. Subjects dropping out before feeling comfortable returning to social engagement will also be censored at 23:59 on the target date of their telephone call visit or date of withdrawal, whichever comes first. The target date can be calculated by taking the date of treatment + 72 hours.

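### Subjects who never answer the 72-hour call are counted as not yet returned for about three days, which pushes the estimated time to social engagement upward

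*Protocol*

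**What the plan says.** **When the question is asked.** Protocol 8.3.1 (Visit 2) asks it at the call after initial treatment: "Interview the subject regarding when (in hours after treatment) the subject felt comfortable returning to social engagements". Protocol 8.3.4 (Visit 3a) repeats it for subjects who had a touch-up: "The following should be completed at the telephone contact 72 hours (± 24 hours) after touch-up". SAP 3.2.4.9 agrees: "A follow-up telephone call should be made 72 hours after each treatment". With the ± 24-hour window, a call can fall anywhere from 48 to 96 hours after injection. The visible lists for the next on-site visits, Protocol 8.3.2 (Visit 2a) and 8.3.5 (Visit 3b), do not contain the question.

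**How subjects without a return time are handled.** SAP 3.2.4.9 gives each group a censoring time. Two rules matter here:

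- Call not answered: "Subjects who never respond to the 72-hour phone call will be censored at 23:59 on the target date of their telephone call visit". The target date is defined as treatment plus 72 hours.
- Reached, but not yet comfortable: "Subjects who never feel comfortable returning to social engagement will be censored at 23:59 on the date of their telephone call visit".

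**Which visit is the call.** In the not-yet-comfortable rule, SAP 3.2.4.9 names Visit 2a as the telephone visit after initial treatment. Protocol 8.3.1 and SAP Table 6 (Section 4.2) make the call Visit 2. Protocol 8.3.2 describes Visit 2a as an on-site visit: "The following should be completed at the follow-up visit 14 days (+7 days) after the Baseline/Initial treatment/Day 1 visit".

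**The concern.** Right-censoring at a given time states that the subject was observed up to then and had not had the event. That is true of someone who says at the call that they are not yet comfortable. It is not true of someone who was never reached. That person may have gone back to work the next morning, and the record is silent from the moment of injection. Censoring at the 72-hour target keeps the subject in the risk set through the hours when most returns may happen, with no possibility of an event. The curve falls too slowly and the median comes out too long.

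Two smaller problems sit in the same section. Censoring not-yet-comfortable subjects at 23:59, instead of when they were spoken to, adds the unobserved rest of that day. The Visit 2a label, read literally, holds the same subjects event-free until Day 14 or later, at a visit whose list does not ask the question.

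At stake is how this endpoint describes downtime. The primary non-inferiority test is not affected.

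**Working it through.** The documents state no figure for this endpoint, so there is none to reproduce. All rates below are assumptions.

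**1. Effect of the missed-call rule.** Let *u* be the share of subjects never reached, *S(t)* the true share not yet returned at time *t*, and *m* the true median. Assume missed calls are unrelated to recovery. Before 48 hours no reached subject is censored by the call, so the Kaplan-Meier estimate under the SAP rule is

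S\*(t) = u + (1 − u)·S(t).

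Setting S\*(t) = 0.5 with exponential times gives

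estimated median = m · log2[ 1 / (1 − 0.5/(1 − u)) ].

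With m = 24 h:

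- u = 0.05: 0.5/0.95 = 0.5263; 1 − 0.5263 = 0.4737; log2(1/0.4737) = 1.078; median = **25.9 h**.
- u = 0.10: 0.5/0.90 = 0.5556; 1 − 0.5556 = 0.4444; log2(1/0.4444) = 1.170; median = **28.1 h**.

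Share not returned at 72 h, taking every call at 72 h: the true value is 0.5^(72/24) = 12.5%. Under the rule it is 0.05 + 0.95 × 0.125 = 16.9% at 5% missed, and 0.10 + 0.90 × 0.125 = 21.3% at 10% missed.

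**2. Check by simulation.** This used 400,000 subjects per scenario, Weibull times, calls uniform over 48–96 h, and calls missed at random. Medians in hours for shape 1 (exponential):

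| Not comfortable at 72 h | Calls missed | True | SAP rule | Never-asked subjects given no event-free time |
|---|---|---|---|---|
| 5% | 5% | 16.6 | 17.9 | 16.6 |
| 10% | 10% | 21.7 | 25.3 | 21.7 |
| 20% | 15% | 31.0 | 39.5 | 30.9 |

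Across shapes 0.8, 1.0 and 1.5, the upward shift in these three scenarios runs from 1.1 h (11.6 to 12.7) to 9.1 h (25.1 to 34.2). Giving never-asked subjects no event-free time brings the median back to within 0.1 h of the truth.

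**3. Does a single call bias the estimate?** With no missed calls and not-yet-comfortable subjects censored at the call, the Kaplan-Meier median equals the true median: 16.7, 21.6 and 31.0 h at 5%, 10% and 20% not comfortable at 72 h (shape 1). Dropping everyone without a return time would lower it, to 15.3, 18.4 and 22.4 h.

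**4. The Visit 2a label.** Take exponential times with a 24-hour median and all calls at 72 h. Then 12.5% are not yet comfortable when called. Read literally, the SAP holds the curve flat at 12.5% until Day 14 (336 h), where the assumed distribution leaves 0.5^(336/24) = 0.5^14 = 0.006%. A median reached before the call would not move, but the tail would be wrong.

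**The case against.** The strongest defence is that SAP 3.2.4.9 leaves nobody without a handling rule. Treating unreached subjects as not returned could also be meant as a cautious choice. The first part stands: the endpoint is right-censored, not truncated. The second does not rescue the rule. The SAP does not present it as an imputation, and in a comparison of two arms its effect depends on how many calls each arm misses, so it is not reliably cautious.

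Stronger readings are tempting, and the documents do not support them:

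- *A reader might infer that asking only once per treatment makes the times too long.* It does not. Return times after the call are unobserved, which limits what can be said beyond about 48–96 hours, but step 3 shows no bias up to the call.
- *A reader might infer from Protocol 5.3.3 that many subjects are still recovering at 72 hours.* The sentence is "Typically, resolution is spontaneous within two to four weeks after injection into the skin". It gives an outer range for local reactions, says nothing about comfort in public, and the daily diary follows those reactions for 28 days.
- *A reader might infer that unblinded staff would miss more calls in one arm.* Nothing in the documents indicates this, and the 48-hour window leaves room for repeat attempts.

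It is also fair to say that consequences are small. SAP 9.2 gives p-values other than the primary only as an aid to interpretation. Finally, the schedule of events, parts of some visit lists and the analysis section for this endpoint are not visible, so the absence of a later enquiry rests on the visible text.

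**Conclusion.** The missed-call rule in SAP 3.2.4.9 is wrong as written. It treats subjects of unknown status as known not to have returned for about 72 hours, and it lengthens the estimated time to return. An assumed 24-hour median becomes 25.9 h at 5% missed calls and 28.1 h at 10%. Over the wider simulated range of 5–15% missed, the shift is about 1 to 9 h.

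These sizes rest on assumed distributions and missed-call rates, on calls being missed independently of recovery, and on a Kaplan-Meier analysis. The last is inferred from the abbreviation list in SAP Section 1 and from the censoring rules. The direction of the bias does not depend on the particular rates, provided missed calls are unrelated to recovery.

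The Visit 2a label is a plain inconsistency to be reconciled. The point is minor for the trial as a whole but cheap to correct.

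**What to change.** In SAP 3.2.4.9:

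1. Let subjects who were never asked contribute no event-free time, either by censoring them at treatment or by excluding them. Both give the same Kaplan-Meier curve. Report their number by arm, so that a reader can judge whether missed calls matter. SAP Section 6 already plans counts of missed visits.
2. Censor subjects not yet comfortable at the time of the call, not at 23:59 that day. If the eCRF holds only the call date, state the convention used.
3. Reconcile the Visit 2a label with Protocol 8.3.1 and SAP Table 6.

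The cost is a few sentences and a change to the derivation program before database lock. No new data are needed. Repeating the question at Visits 2a and 3b for subjects without a return time is optional. It would extend the horizon at the price of mixing two recall periods, and the bias is removed without it.
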